| case selection      | 
Inclusion criteria:
 
(1) diagnosis of septic shock in accordance with the Surviving Sepsis Campaign International; (2) receipt of initial fluid resuscitation in the emergency department with a hospital stay of at least 6 hours; (3) age <math>\geq</math> 18 years; (4) provision of informed consent.
 
excluded criteria:
 
(1) contraindications to rapid fluid administration (e.g., end-stage renal disease, end-stage heart failure, acute pulmonary edema); (2) inability to comply with treatment, such as patients with severe trauma, burns, cancer undergoing chemotherapy, pregnant or lactating women, and those with mental illness; (3) withdrawal from treatment or transfer to another facility within 24 hours of admission.
 |
| Treatment plan      | 
Both groups were managed according to the 2021 Surviving Sepsis Campaign (SSC) International Guidelines for septic shock resuscitation, including: (1) early antimicrobial therapy, (2) vasopressor support (with norepinephrine as first-line), and (3) organ function support. The key difference between groups lay in the fluid resuscitation monitoring approach (critical care ultrasound vs. noninvasive cardiac output monitoring)
   |
| efficacy evaluation | 
The main efficacy indicators: emergency department length of stay, total hospital stay.
 
Secondary efficacy indicators: regarding total fluid volume within the first 6 hours of resuscitation, early resuscitation efficacy (time to achieve mean arterial pressure <math>\geq</math>65 mmHg, lactate reduction <math>\geq</math>20% from baseline, or lactate clearance <math>\geq</math> 10%), complication rates (including pulmonary edema, renal injury, and acute respiratory distress syndrome).
   |

|                           |  |
|---------------------------|--|
|                           | Safety evaluation index: 28-day mortality.   |

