### **(6) Observation items and detection time points**

1. Demographic data of patients, including gender, age, and underlying diseases, were collected, along with mean arterial pressure, baseline lactate levels, and vital signs at enrollment.
2. Records were made of the total fluid volume administered within the first 6 hours after patients were randomized into groups, the achievement of resuscitation targets, blood

lactate levels, blood pressure, and the incidence of complications such as pulmonary edema and renal injury.

3. Document the use of vasoactive agents (e.g., dopamine, epinephrine/norepinephrine), mechanical ventilation support, and antibiotics.
4. Record the duration of Emergency Department stay, total hospital stay, 28-day mortality, and adverse events occurring during the study period (e.g., severe arrhythmias, anaphylactic shock).

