## **(10)Statistical processing**

This study adopted a prospective randomized controlled design, and the sample size was estimated using PASS 15.0 software. Based on the difference in 6-hour fluid resuscitation volume between the two groups in the pilot study (mean difference 1261 mL, standard deviation 3155 mL),  $\alpha=0.05$  (bilateral) was set  $\beta=0.2$ , Calculated to require 27 cases per group, considering a 20% dropout rate, 60 cases were ultimately included. Use SPSS 26.0 to generate block random sequences (block size 4), and allocate concepts through sealed envelopes. The normality of the measurement data was confirmed by Shapiro Wilk test, and those that conform to the normal distribution were expressed as mean  $\pm$  standard deviation. Independent sample t-test was used for inter group comparison; non normally distributed individuals are represented by the median (interquartile range) and Mann Whitney U test is used. The categorical data is presented in terms of the number of cases (%), and the comparison between groups is conducted using the chi square test or Fishers exact test (when the theoretical frequency is less than 5). The main outcome (28 day mortality rate) was plotted using Kaplan Meier survival curve, and inter group differences were analyzed using log rank test, and HR (95% CI) was calculated. Secondary outcomes (such as fluid dosage, MAP, etc.) report mean difference (MD) or relative risk (RR) and their 95% confidence intervals. All tests are bilateral, and  $P<0.05$  is considered statistically significant. Perform Bonferroni correction on secondary outcomes ( $\alpha=0.05/6 \approx 0.008$ ). Multivariate Cox regression was used to adjust for confounding factors such as age and baseline lactate, and sensitivity analysis included protocol set (PP) and intention to treat (ITT) analyses. The statistical software used is R 4.3.1 (R Foundation) and SPSS 26.0 (IBM).

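### MAP is to be reported as an unadjusted mean difference although each patient's enrolment MAP is recorded; adjusting for it costs no data, with a gain from nil to large depending on a correlation the protocol does not give

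*Protocol*

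**What the plan says.** The rule for continuous outcomes is in Protocol section (10), Statistical processing, and is repeated in the statistical method row of the synopsis. After a Shapiro-Wilk test, normal data follow the rule "Independent sample t-test was used for inter group comparison"; for the rest, "non normally distributed individuals are represented by the median (interquartile range) and Mann Whitney U test is used". On effect measures the section says "Secondary outcomes (such as fluid dosage, MAP, etc.) report mean difference (MD) or relative risk (RR) and their 95% confidence intervals". No covariate is named for any continuous outcome. The only stated adjustment is a Cox model with factors such as age and baseline lactate. Its outcome is not named, but 28-day mortality is the only outcome the section analyses as time to event.

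Section (6), item 1, collects demographic data "along with mean arterial pressure, baseline lactate levels, and vital signs at enrollment". Item 2 records, after randomisation, "lactate levels, blood pressure, and the incidence of complications such as pulmonary edema and renal injury". Randomisation is in blocks of four, with no stratification by MAP or lactate stated.

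The efficacy evaluation row of the synopsis describes the same variables differently. MAP appears as "time to achieve mean arterial pressure" of at least 65 mmHg. Lactate appears as a "lactate reduction" of at least 20% from baseline, or a clearance of at least 10%.

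**The concern.** When the enrolment value of an outcome is already recorded, comparing follow-up values without it discards information. In a trial of about 30 per arm with no stratification on the variable, the arms can differ at baseline by chance. Part of that difference then appears in the estimated effect.

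Two things are at stake for MAP: a wider confidence interval than the same data could give, and an estimate that cannot be separated from baseline imbalance in the sample actually drawn. The plan already uses baseline lactate as a covariate in its Cox model, so leaving the enrolment value out of the MAP comparison is not a consequence of missing data. Nor is it a detail left open for a later plan, because the protocol names the tests.

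**Working it through.** **Inputs from the protocol.** 30 per group (synopsis); two-sided 0.05; secondary outcomes at 0.05/6 = 0.0083, which agrees with the stated approximation of 0.008. **Assumption.** The baseline-to-follow-up correlation r is not in the documents, so a range of 0.1 to 0.7 is shown.

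The protocol's 27 per group is a calculation for 6-hour fluid volume, not MAP. It does not reproduce: 2 × (1.96 + 0.84)² × (3155/1261)² gives 99 per group. That is a separate problem, and nothing below depends on it.

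**Step 1: precision.** Analysis of covariance multiplies the variance of the mean difference by 1 − r². Estimating the slope costs one degree of freedom, a factor of about 57/56 with 60 patients. The interval width scales with √(1 − r²), and 60 adjusted patients are worth 60/(1 − r²) unadjusted ones (both ignoring the 57/56 factor).

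| r (assumed) | 1 − r² | × 57/56 | interval width | worth of 60 patients |
|---|---|---|---|---|
| 0.1 | 0.99 | 1.01 | 0.99 | 61 |
| 0.3 | 0.91 | 0.93 | 0.95 | 66 |
| 0.5 | 0.75 | 0.76 | 0.87 | 80 |
| 0.7 | 0.51 | 0.52 | 0.71 | 118 |

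**Step 2: chance imbalance.** The standard error of a baseline difference is SD × √(2/30) = 0.258 SD, so its 95% range is ±1.96 × 0.258 = ±0.51 SD. A baseline difference d shifts the unadjusted result by r × d. At d = 0.51 SD the shift is 0.05, 0.15, 0.25 and 0.35 SD for r = 0.1, 0.3, 0.5 and 0.7.

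**Step 3: type I error given the imbalance.** With s = 0.258, the probability that the unadjusted test rejects at 0.05 under no effect is 1 − Φ[(1.96s − rd)/(s√(1 − r²))] + Φ[(−1.96s − rd)/(s√(1 − r²))].

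| r | d = 0.26 SD | d = 0.51 SD |
|---|---|---|
| 0.1 | 5.0% | 5.3% |
| 0.3 | 5.0% | 7.9% |
| 0.5 | 4.8% | 12.9% |
| 0.7 | 3.9% | 20.5% |

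An imbalance of one standard error does not raise the error rate above 5%. One at the edge of the 95% range does, materially so once r is 0.3 or more.

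**Step 4: does the 0.05/6 threshold change the picture?** The gains in step 1 do not depend on the threshold. Power gains do, but the direction depends on an effect size that must also be assumed. With 30 per group and r = 0.5:

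- For a 0.74 SD effect, power rises from 59% to 75% at 0.05/6 and from 82% to 91% at 0.05.
- For a 0.5 SD effect, it rises from 24% to 34% at 0.05/6 and from 49% to 61% at 0.05.

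The gain is larger at the stricter threshold in the former case and slightly smaller in the latter.

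**The case against.** The strongest reply is that a valid unadjusted comparison of a secondary outcome is not an error, and that covariates are often settled in an analysis plan, which may exist here but is not shown. The first half stands: over randomisation the test is unbiased and holds its type I error. The second half does not remove the point, because section (10) states the tests rather than leaving them open.

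A second reply is that the benefit may be negligible. Both arms receive vasopressor support, and fluids are adjusted until resuscitation targets are met, so follow-up MAP may depend little on enrolment MAP. This stands. At r = 0.1 there is no gain.

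A third reply is that the remedy does not fit the endpoints as written. The synopsis makes MAP a time to target. No follow-up time is clearly set for blood pressure or lactate, since the 6-hour window in section (6) is attached to fluid volume. This narrows the fix, but the MAP mean difference in section (10) remains unadjusted.

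A reader might also infer that lactate is to be compared by t-test. No section says so by name. Lactate is not among the examples given for mean differences, and its defined endpoint is a threshold against the patient's own baseline. Raw lactate levels come under the t-test or Mann-Whitney rule only so far as they are compared at all. The threshold uses the baseline value, but it is not a model adjustment and does not remove imbalance.

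**Conclusion.** The point holds as an improvement available without new data, not as a fault that invalidates the analysis. It applies firmly to MAP, which section (10) names as a mean-difference outcome. It applies to lactate only if lactate levels are compared as a continuous outcome.

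The size rests entirely on the assumed correlation: a variance factor of about 1.01 at r = 0.1, falling to about 0.52 at r = 0.7. Three stronger readings are not supported:

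- That the unadjusted test is biased. It is not over randomisation; the exposure is conditional on the imbalance that occurs.
- That imbalance passes straight into the result. It passes in scaled by r.
- That the 0.05/6 threshold by itself makes adjustment more valuable. Step 4 shows that this depends on the effect size.

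**What to change.** In section (10) and in the statistical method row of the synopsis, state that MAP, and any continuous lactate comparison (log scale if skewed), is analysed at a named follow-up time by analysis of covariance. Arm is the factor and the patient's own enrolment value is the covariate. Report the adjusted mean difference with its 95% confidence interval; on the log scale it back-transforms to a ratio. Fix this before outcome data are analysed.

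The same edit must reconcile section (10) with the efficacy evaluation row of the synopsis: say whether MAP is a time to target, a level at a stated time, or both, and whether lactate is analysed only as a threshold or also as a level. The investigators need to choose and state the follow-up time.

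The cost is about a sentence in each of the two places plus the reconciliation of the definitions. Enrolment values are already collected, so no new patients or baseline measurements are needed.

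### Power for 6-hour fluid volume is set at alpha 0.05, but the protocol tests that outcome at 0.05/6, so the stated 80% does not describe the planned test

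*Protocol*

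**What the plan says.** The sample-size text stands in section (10) and again in the statistical-method row of the synopsis. The calculation is "Based on the difference in 6-hour fluid resuscitation volume between the two groups in the pilot study", with a mean difference of 1261 mL, an SD of 3155 mL, two-sided alpha 0.05 and beta 0.2. Its result is "Calculated to require 27 cases per group, considering a 20% dropout rate, 60 cases were ultimately included".

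Later in the same paragraph, fluid volume is the first example of a secondary outcome: "Secondary outcomes (such as fluid dosage, MAP, etc". The multiplicity rule is then "Perform Bonferroni correction on secondary outcomes", with alpha 0.05/6, printed as about 0.008. Continuous outcomes are compared by t-test if normal; otherwise "non normally distributed individuals are represented by the median (interquartile range) and Mann Whitney U test is used".

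The efficacy row of the synopsis also places fluid volume among the secondary outcomes: "Secondary efficacy indicators: regarding total fluid volume within the first 6 hours of resuscitation".

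The document disagrees on what is primary. Sections (7) and (10) name 28-day mortality. The synopsis says "The main efficacy indicators: emergency department length of stay, total hospital stay" and lists mortality under safety: "Safety evaluation index: 28-day mortality". Fluid volume is not primary in any of these places.

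**The concern.** A power statement holds only for the significance level at which it was computed. Here one outcome has two levels in one paragraph: 0.05 for sizing and 0.05/6 for testing. The stricter level lowers power, so beta 0.2 cannot be the type II error of the planned test.

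This matters because fluid volume is the only outcome for which the protocol gives any power basis. If the comparison misses significance at 0.05/6, a reader who turns to the protocol finds beta 0.2 and may take the result as fairly strong evidence against a 1261 mL difference. The planned test would not support that reading.

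**Working it through.** **Inputs.** Difference 1261 mL, SD 3155 mL, two-sided alpha 0.05, beta 0.2, 27 per group, 60 in total and 20% dropout, from section (10). Test level 0.05/6 = 0.00833, same section. The 73 participants come from section (3); their split of 36/37 is an assumption.

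**Standardised difference.** d = 1261/3155 = 0.3997, so d² = 0.1598.

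**The plan's own figure.** n per group = 2(z₁₋α/₂ + z₀.₈)²/d². At alpha 0.05 this is 2(1.960 + 0.842)²/0.1598 = 98.3, so 99 (100 with the t distribution). The stated 27 is not reproduced. That is a separate fault, kept apart below.

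**Power of the t-test.** The noncentrality is d√(n/2) with 2n − 2 degrees of freedom. At 27 per group it is 0.3997 × √13.5 = 1.469. The critical value is 2.007 at 0.05 and 2.743 at 0.05/6, which gives power 0.302 and 0.112.

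| Per group | Power at 0.05 | Power at 0.05/6 |
|---|---|---|
| 24 (30 less 20% dropout) | 27% | 10% |
| 27 | 30% | 11% |
| 30 | 33% | 13% |
| 36/37 (assumed split of 73) | 39% | 17% |
| 100 | 80% | 56% |
| 154 | 94% | 80% |

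**Size needed at the level used.** 2(2.638 + 0.842)²/0.1598 = 151.6, so 152 per group (154 with the t distribution), before dropout.

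**Detectable difference.** With 27 per group, SD 3155 mL and 80% power, it is 0.777 × 3155 = 2451 mL at 0.05 and 0.980 × 3155 = 3092 mL at 0.05/6, against the 1261 mL assumed.

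**Separating the two faults.**

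- *Size error repaired at 0.05 only.* 100 per group gives 80% at 0.05 and 56% at 0.05/6.
- *Size error conceded.* Suppose 27 per group does give 80% at 0.05. This implies d = 0.777, an assumption that is not in the protocol. Power at 0.05/6 is then 55% with 27 per group and 61% with 30.

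In both cases the alpha mismatch alone costs about 25 percentage points.

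**Other variants.** Using the printed 0.008 in place of 0.00833 gives 10.9% at 27 per group. A simulation of the Mann-Whitney test on normal data gave 28% and 10% at 27 per group, and 31% and 11% at 30.

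**The case against.** The inconsistency and the t-test figures are not in dispute; the case on the other side concerns weight and remedy.

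*It follows from larger faults.* The size does not follow from its inputs, and the trial is sized on an outcome that is not primary while the primary itself is contradictory. If the trial were re-sized on a settled primary, or fluid volume were made primary, the mismatch would go. That is true, but the present text does neither, and the more obvious repair, correcting the arithmetic at 0.05, leaves the mismatch in place.

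*Family membership is inferred.* The six outcomes behind 0.05/6 are never listed, and the secondary list in section (7) does not name fluid volume. This stands as a limit. However, section (10) and the synopsis both call fluid volume secondary, and the correction applies to secondary outcomes without exception. The general P<0.05 sentence comes just before the specific rule and does not override it.

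*Attribution.* It would be unfair to charge the whole fall from 80% to 11% to this point. That is accepted: only the step from 30% to 11% (or from 80% to about 55% in the conceded case) belongs here.

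*Choice of figures.* The Mann-Whitney simulation used normal data, whereas the plan uses that test for non-normal data, so it is only a rough guide and the conclusion does not rest on it. The 30 and 36/37 rows assume no dropout; the 24 row shows the planned loss, and power there is lower still.

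*How a null result would be read.* No passage says it would be set against 80% power. This too is fair: it is a foreseeable misreading, not a stated intention.

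**Conclusion.** The point holds. The implied 80% power does not apply to the test that the protocol prescribes for 6-hour fluid volume. With the protocol's inputs and a t-test, power at 0.05/6 is 11% with 27 per group and 13% with 30, against 30% and 33% at 0.05. The mismatch remains whether the separate sample-size error is repaired (56%) or conceded (55%). This rests on equal SDs and normal data for the power figures, and on fluid volume being in the corrected family, as section (10) and the synopsis indicate. It should be put right, but it does not invalidate the test itself.

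**What to change.** In section (10) and in the statistical-method row of the synopsis, restate the power or the detectable difference for 6-hour fluid volume at 0.05/6, in the same revision that corrects the sample-size figure. Add that a non-significant result on fluid volume will not be interpreted against 80% power.

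The cost is protocol wording; tests, multiplicity rule and outcome hierarchy are unchanged by this point. The downside is a less favourable figure: 11% with 27 per group, of which only the step down from 30% is due to the alpha mismatch. The alternatives are larger changes. Keeping 80% at 0.05/6 would need 154 per group before dropout. Moving fluid volume out of the corrected family would change the hierarchy and could be justified only if decided without knowledge of the results.

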# **Clinical research protocol**

Project name: The value of critical care ultrasound and noninvasive cardiac output monitoring in guiding fluid resuscitation for septic shock in the emergency department

leading unit:Guangzhou Panyu Central Hospital, Guangzhou, Guangdong, China

project leader:[name]

Department: Emergency Department

Research period: July 2025 to July 2025

Version No.: V 1.0

Version Date: May 22, 2023

|                                      |   |
|--------------------------------------|---|
| object name                          | The value of critical care ultrasound and non-invasive cardiac output monitoring in fluid resuscitation for emergency department patients with septic shock.  |
| goal of study                        | This study explores the value of critical care ultrasound and non-invasive cardiac output monitoring in fluid resuscitation for emergency department patients with septic shock, providing evidence for optimizing hemodynamic management of septic shock, improving patient prognosis, and guiding clinical selection of appropriate monitoring modalities.  |
| research design               | Subjects were recruited from patients with septic shock admitted to the Emergency Department of Guangzhou Panyu District Central Hospital between July 2023 to July 2025. Demographic data of patients, including gender, age, and underlying diseases, were collected, along with mean arterial pressure, baseline lactate levels, and vital signs at enrollment. Records were made of the total fluid volume administered within the first 6 hours after patients were randomized into groups, the achievement of resuscitation targets, blood lactate levels, blood pressure, and the incidence of complications such as pulmonary edema and renal injury. Additionally, the use of vasoactive agents (e.g., dopamine, epinephrine/norepinephrine), mechanical ventilation support, and antibiotics was documented. Patients were followed up to record the duration of emergency department stay, total hospital stay, 28-day mortality, and adverse events occurring during the study period (e.g., severe arrhythmias, anaphylactic shock). |
| Total number of cases studied | 60 cases (30 cases in each group)   |

|                            |   |
|----------------------------|---|

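### Holm's step-down procedure could replace single-step Bonferroni for the secondary outcomes at no cost: the same family-wise error, never fewer rejections, and a gain in power that is small at the protocol's own effect size

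*Protocol*

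**What the plan says.** Section (10), Statistical processing, instructs: "Perform Bonferroni correction on secondary outcomes", with the level given as "\alpha=0.05/6 \approx 0.008". The statistical method row of the synopsis repeats this. No stepwise procedure is mentioned, so each secondary outcome faces the same threshold whatever the other outcomes show.

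The same section states "All tests are bilateral" and sets P<0.05 as the general level. It calls 28-day mortality the main outcome, which leaves mortality outside this correction. For secondary outcomes it plans a mean difference or "relative risk (RR) and their 95% confidence intervals".

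The synopsis gives the size as "60 cases (30 cases in each group"). The only effect size in the document is the one for 6-hour fluid volume, which the synopsis lists among the secondary indicators: "mean difference 1261 mL, standard deviation 3155 mL".

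**The concern.** Bonferroni keeps all six thresholds at 0.05/6 even after some null hypotheses have been rejected. Holm relaxes the threshold after each rejection and still holds the family-wise error at 0.05 without further assumptions. For testing alone, single-step Bonferroni is therefore dominated.

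The secondary outcomes named in the synopsis (fluid volume, early resuscitation targets, complications) describe one resuscitation process. If the monitoring methods differ at all, several outcomes may move together, and that is the situation in which Holm gains. At stake is whether second and later real differences can be declared in a trial of 60 patients.

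**Working it through.** **Inputs.** From the protocol: six tests, family level 0.05, two-sided, 30 per arm, standardised difference 1261/3155 = 0.40. Assumed: correlation 0.3 between outcomes, other standardised differences of 0.6 and 0.8, the number of real effects, and approximately normal test statistics.

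**1. The protocol's figure.** 0.05/6 = 0.00833, or 0.008 to three decimals. It reproduces. The family-wise error is at most 6 × 0.00833 = 0.05, and at most 6 × 0.008 = 0.048 with the rounded value.

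**2. Holm's thresholds.** The ordered P values are compared with 0.05/6, 0.05/5, 0.05/4, 0.05/3, 0.05/2 and 0.05/1, that is 0.0083, 0.0100, 0.0125, 0.0167, 0.025 and 0.05. Testing stops at the first failure.

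- *Never rejects less.* An outcome with P ≤ 0.0083, and every outcome with a smaller P value, passes its step, because no step is stricter than 0.0083.
- *Same error control.* Suppose k of the six null hypotheses are true. The first true null to be rejected is reached no later than step 6 − k + 1, where the threshold is at most 0.05/k. The chance that any of the k true nulls has a P value that small is at most k × 0.05/k = 0.05, under any dependence.

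**3. Power under Bonferroni.** The noncentrality is d × √(30/2) = d × 3.873, and the two-sided critical value at 0.00833 is 2.638.

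- d = 0.40: Φ(1.549 − 2.638) = Φ(−1.089) = 13.8%
- d = 0.6: Φ(2.324 − 2.638) = Φ(−0.314) = 37.7%
- d = 0.8: Φ(3.098 − 2.638) = Φ(0.460) = 67.7%

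**4. Power under Holm, by simulation** (six correlated two-sided z-tests, correlation 0.3, at least 100,000 runs per scenario). Average power per real effect:

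| Standardised difference | Bonferroni | Holm, 1 real effect | Holm, 3 real effects | Holm, 6 real effects |
|---|---|---|---|---|
| 0.40 (protocol) | 14% | 14% | 15% | 16% |
| 0.6 (assumed) | 38% | 38% | 40% | 46% |
| 0.8 (assumed) | 68% | 68% | 71% | 79% |

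With two real effects the gain is under half a point at 0.40 and about 1.5 points at 0.8. In no run did Bonferroni reject an outcome that Holm did not. Family-wise error over the true nulls stayed below 5% for both methods.

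**5. Other measures of power.** The chance of at least one true rejection differs by no more than about 0.1 point; for example, it is 92.3% for both methods with three real effects of 0.8. The chance of showing every real effect moves more. With three effects it goes from 1.3% to 2.1% at 0.40 and from about 38% to 45% at 0.8. With six effects of 0.8 it goes from 22% to about 52%.

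**6. Intervals.** Intervals that match the Bonferroni tests would have level 1 − 0.05/6 = 99.17%. The protocol plans 95%, so it does not draw on that advantage.

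**The case against.** The strongest reply is that nothing here is wrong. Bonferroni is valid, prespecified, worded identically in both places and correctly computed. Advice to use Holm fits any plan that uses Bonferroni. All of that stands, and it is why the point is an optional improvement.

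A reader might infer that the trial throws away substantial power. The documents do not support this. The large gains need a standardised difference of 0.8, twice the only one in the protocol, and several or all of the six outcomes truly different. At 0.40 the average gain is about 0 to 2 points. Holm relaxes a threshold only after another outcome has passed 0.0083, so with one real effect it gains almost nothing. Some outcomes are binary complications, so the simulated sizes are indicative only. The ordering of the two methods does not depend on that.

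Two further objections hold in part. First, the six outcomes are not listed, so Holm cannot be applied until they are. The same is true of the divisor 6, and this is a separate matter. Second, Holm may reject an outcome whose Bonferroni-level simultaneous interval still includes no effect. This is a small real cost, but the protocol does not plan such intervals.

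**Conclusion.** The point holds as a free improvement. The single threshold of about 0.008 is valid and correctly derived. Holm gives the same family-wise guarantee under any dependence and never rejects less, and the protocol does not use what Bonferroni offers in exchange.

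The gain in average power runs from nil (one real effect) to about 2 points (six real effects) at 0.40, and to about 11 points (six real effects) at 0.8. These figures rest on 30 evaluable patients per arm, correlation 0.3 and equal real effects.

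It should not be read as a remedy for low power. At the protocol's own inputs, 2 × (1.960 + 0.842)² × (3155/1261)² gives 99 per group at two-sided 0.05 and 80% power, against the stated 27. That shortfall comes from the sample size, and no multiplicity procedure repairs it.

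**What to change.** In section (10) and in the statistical method row of the synopsis, replace the Bonferroni sentence with: *Secondary outcomes are tested with Holm's step-down procedure at family-wise two-sided 0.05.* Apply it to the same family of secondary outcomes.

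Make the change before any comparative results are seen. If any have been seen, keep the prespecified Bonferroni rule. If simultaneous intervals are later wanted, 99.17% intervals remain valid, with a note that they may not agree with every Holm rejection.

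The cost is one sentence in two places, with no extra patients, data or staff.

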## **(7) standards for efficacy appraisal**

The primary outcome was 28-day mortality

Secondary outcomes included the efficacy of initial resuscitation, duration of hospital stay, incidence of complications, and other relevant parameters.

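### The Bonferroni divisor of 6 cannot be traced to any enumerated list of secondary outcomes, and the list is left open, so 5% family-wise control is not assured

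*Protocol*

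**What the plan says.** Section (10), and the statistical method row of the synopsis in the same words, instruct: "Perform Bonferroni correction on secondary outcomes", with a threshold of 0.05/6, rounded to 0.008. The sentence before it sets the general rule: "All tests are bilateral, and" a P value below 0.05 counts as significant.

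The outcomes are described in three places, and the descriptions differ.

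- **Synopsis, efficacy evaluation.** Length of stay comes first: "The main efficacy indicators: emergency department length of stay, total hospital stay". The secondary list has three headings. The first two are "regarding total fluid volume within the first 6 hours of resuscitation, early resuscitation efficacy (time to achieve mean arterial pressure" and so on, where the second heading goes on to two lactate criteria joined by an or: "20% from baseline, or lactate clearance". The third is "complication rates (including pulmonary edema, renal injury, and acute respiratory distress syndrome". 28-day mortality is listed as a safety index.
- **Section (7).** "The primary outcome was 28-day mortality". The secondary outcomes are initial resuscitation efficacy, then "duration of hospital stay, incidence of complications, and other relevant parameters". Fluid volume is not named.
- **Section (10).** 28-day mortality is the main outcome. Secondary outcomes are indicated only by two examples, fluid dosage and MAP, followed by an et cetera.

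**The concern.** A Bonferroni divisor is the size of a closed family of tests. Here the divisor is fixed, but the family differs between sections and is open in two of them. A reader cannot tell which six tests the 0.008 threshold governs, or whether there are six.

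Two things are at stake. First, 0.008 is the decision rule for every secondary claim, including 6-hour fluid volume, the quantity on which the sample size is based. If more than six tests are made, the rule may not hold the 5% it is set to hold; if fewer, it is stricter than it need be. Second, the same comparison can fall under two thresholds. Total hospital stay is a main indicator in the synopsis and a secondary outcome in section (7), so a result of P = 0.02 would be significant under one and not under the other.

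**Working it through.** **1. The plan's own figure.** 0.05/6 = 0.00833, which rounds to 0.008. The arithmetic reproduces; the question is where the 6 comes from.

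**2. Counting the family.**

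| Reading | Count |
|---|---|
| Synopsis, by heading (fluid volume; early resuscitation; complications) | 3 |
| Section (7), by category | 3, plus an open item |
| Synopsis, one of the two grouped headings split (1 + 3 + 1) | 5 |
| Synopsis, all split, the two lactate criteria taken as one (1 + 2 + 3) | 6 |
| Synopsis and section (7) merged: fluid volume, resuscitation composite, hospital stay, three complications | 6 |
| Synopsis, every item separate (1 + 3 + 3) | 7 |
| Synopsis, every item separate, plus ED stay and hospital stay (7 + 2) | 9 |

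Six can be reached, but only by a choice that the protocol does not state.

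**3. Family-wise error at 0.008 per test.** The bound under any dependence is k × 0.008. With independent tests of exact size 0.008 it is 1 − (1 − 0.008)^k.

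| k | Bound | Independent tests | Bonferroni threshold for that k, 0.05/k |
|---|---|---|---|
| 3 | 2.4% | 2.4% | 0.0167 |
| 5 | 4.0% | 3.9% | 0.0100 |
| 6 | 4.8% | 4.7% | 0.0083 |
| 7 | 5.6% | 5.5% | 0.0071 |
| 9 | 7.2% | 7.0% | 0.0056 |

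With the unrounded 0.05/6, the bound is 5.8% at k = 7 and 7.5% at k = 9. The 5% level is passed only from seven tests on.

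**4. Tests that do not reach their nominal size.** Section (10) sends categorical outcomes to Fisher's exact test when an expected frequency is below 5. With 30 per arm that means a pooled rate below 5/30, about 17%. Complication rates are not given, so 5%, 10% and 15% are assumptions. At nominal 0.008, Fisher's actual size is then 0.00004, 0.0008 and 0.0021. Take three complications tested this way and all other tests independent at the full 0.008:

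- Seven tests: from 1 − 0.992^4 × (1 − 0.00004)^3 = 3.2% to 1 − 0.992^4 × (1 − 0.0021)^3 = 3.8%.
- Nine tests: from 1 − 0.992^6 × (1 − 0.00004)^3 = 4.7% to 1 − 0.992^6 × (1 − 0.0021)^3 = 5.3%.

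These figures assume that Fisher's test is used on every complication table. At higher rates the chi-square test takes over and the relief shrinks.

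**5. Hospital stay.** The threshold is 0.05 as a main indicator (synopsis) and 0.008 as a secondary outcome (section (7)), a ratio of 0.05/0.008, roughly six-fold.

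**The case against.** The strongest reply is that six has a natural source in the synopsis alone. If lactate clearance means the percentage fall from baseline at the same time point, which the protocol does not define, then a 20% fall always meets the 10% criterion. The two criteria are then nested cut-offs of one measure, and fluid volume, MAP time, lactate and three complications make six. This is plausible, and it rules out saying that six is impossible. It remains an inference: the protocol does not state the count, section (7) gives a different set, and both section (7) and section (10) leave the set open.

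A second reply is that listing the family in full is usual SAP content, and an SAP may exist. That would answer a complaint of missing detail. Here the protocol fixes the number itself, twice, beside lists that do not plainly produce it.

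A third is that part of this follows from the conflict over the primary outcome. That is true, and resolving the conflict settles where length of stay belongs. It does not settle how grouped items are counted or close the list.

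A reader might go further and infer that the protocol names 7 to 9 outcomes, so that 0.008 fails to hold 5%. The documents do not support this. Seven requires every component to be tested separately. Nine also needs ED stay, which section (7) does not name and which the synopsis treats as a main indicator, so it combines two conflicting hierarchies. A count of ten, adding MAP, probably counts time to target MAP twice. A reader might also suspect that six outcomes could be picked after seeing the data; no text provides for that, although an open list does not prevent it.

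**Conclusion.** The point holds in a limited form. The divisor of 6 is correct arithmetic on an untraceable count. The protocol supports about 3 to 9 secondary outcomes and leaves the list open, so 5% control is not assured; it is not shown to fail. At 0.008 per test the family-wise error is at most 4.8% for six or fewer tests, and the threshold is conservative for 3 to 5. It is about 5.5% for seven and 7.0% for nine, assuming independent tests of full size. Positive correlation, for example between the lactate criteria, or Fisher tests on sparse complications would lower these figures, possibly below 5% at seven tests. Any excess is therefore modest. The double threshold for hospital stay does not depend on how components are counted: it follows directly from the conflict between the synopsis and section (7).

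**What to change.** Before analysis:

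1. Make the outcome hierarchy the same in the synopsis, section (7) and section (10), so that 28-day mortality, ED stay and hospital stay each have one role.
2. Name one closed secondary family, once, and state whether the resuscitation and complication items are tested separately or as composites.
3. Remove the open-ended items from the tested set and label everything outside the family exploratory. Confine the general 0.05 rule to tests outside the corrected family.
4. Set the correction to the resulting count k and use Holm in place of Bonferroni. Order the P values and compare the smallest with 0.05/k, the next with 0.05/(k − 1), and so on, stopping at the first failure.

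Holm has the same family-wise error as Bonferroni and never less power. The gain is small: in a simulation of seven independent tests with 50% power each under Bonferroni, power rose to 51.1%, 52.3% and 53.6% with two, three and four true effects. Holm does not itself repair the count; steps 1 to 3 do that.

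The cost is wording. The one statistical downside is a slightly stricter first step if more than six outcomes are kept, 0.0071 for seven or 0.0056 for nine, which Holm's later steps partly offset.
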